16.6 Completion of the Study and Definition of Study End Date

The study end date is deemed to be the date of last data capture.

16.7 Archiving

Essential trial documents should be retained according to local policy. Documents should be securely stored and access restricted to authorised personnel.

17 PATIENT PROTECTION AND ETHICAL CONSIDERATIONS

17.1 Trial Approvals

This trial has been formally assessed for risk by ICR-CTSU.

In the UK, ICR-CTSU, on behalf of the Sponsor, will ensure that the trial has received ethics approval from a research ethics committee for multi-centre trials and the Health Research Authority (HRA). Before entering patients, the Principal Investigator at each site is responsible for obtaining local R&D confirmation of site capacity and capability to conduct the trial.

The coordinating group in each country, on behalf of the Sponsor, will ensure that the trial has received all relevant ethical, regulatory and institutional approval prior to the recruitment of any patients.

17.2 Trial Conduct

This trial will be conducted according to the approved protocol and its amendments, supplementary guidance and manuals supplied by the Sponsor and in accordance with relevant national guidelines.

17.3 Informed Consent

Patients should be asked to sign the current ethics approved HALT consent form at trial entry after receiving both verbal and written information about the trial, having been given sufficient time to

consider this information. All consent forms must be countersigned by the Principal Investigator or a designated individual. A signature log of delegated responsibilities, listing the designated individuals and the circumstances under which they may countersign consent forms, must be maintained at the participating site. This log, together with original copies of all signed patient consent forms, should be retained in the Site Investigator File and must be available for monitoring and audit. The current ethics approved HALT patient information sheets should be provided in addition to any standard patient information sheets that are provided by the site and used in routine practice.

17.4 Patient Confidentiality

Patients will be asked to consent to their full name being collected at trial entry in addition to their date of birth, hospital number, postcode and NHS number or equivalent to allow linkage with routinely collected healthcare data and ensure accuracy in handling biological samples.

Each investigator should keep a separate log of all participants' Trial IDs, names, addresses and hospital numbers. The investigator must retain trial documents (e.g. participants' written consent forms) in strict confidence. The investigator must ensure the participants' confidentiality is maintained at all times.

Representatives of ICR-CTSU will require access to participants' hospital notes for quality assurance purposes. ICR-CTSU will maintain the confidentiality of participants at all times and will not reproduce or disclose any information by which participants could be identified.

17.5 Data Protection

ICR-CTSU will comply with all applicable data protection laws.

17.6 Liability

The coordinating group in each country will ensure that appropriate indemnity arrangements are place to meet the potential legal liabilities of investigators conducting the trial.

18 FINANCIAL MATTERS

This trial is investigator designed and led and has been approved by the Clinical Research Committee of Cancer Research UK.

ICR has received funding from Cancer Research UK for the central coordination of the trial. In the UK, the trial meets the criteria for R&D support as outlined in the Statement of Partnership on Non-Commercial R&D in the NHS in England. The trial is part of the National Institute for Health Research Clinical Research Network (NIHR CRN) portfolio. NCRN resources should therefore be made available for the trial to cover UK specific research costs.

The coordinating group in each country will ensure that sufficient funding is available for the coordination and conduct of the trial.

19 PUBLICATION POLICY

The main trial results will be published in a peer-reviewed journal, on behalf of all collaborators. The manuscript will be prepared by a writing group, consisting of members of the TMG. Participating clinicians may be selected to join the writing group on the basis of intellectual and time input. All participating clinicians will be acknowledged in the publication.

Any presentations and publications relating to the trial must be authorised by the TMG. Authorship of any secondary publications e.g. those relating to sub-studies, will reflect intellectual and time input into these studies.

No investigator may present or attempt to publish data relating to the HALT trial without prior permission from the TMG.

20 ASSOCIATED STUDIES

20.1 Translational study

20.1.1 Comparison of archival tumour DNA with ctDNA to assess baseline OPD

Collection and next generation sequencing of archival tumour DNA and ctDNA at baseline to assess the mutational heterogeneity of oligoprogressive NSCLC will be performed. We hypothesize that the different possible mechanisms of resistance to EGFR/ALK TKI may affect sensitivity to SBRT.

20.1.2 Analysis of circulating biomarkers to assess ctDNA kinetics and tumour evolution following SBRT.

The half life of ctDNA is 0.5-2 hours. We intend to assess the release of ctDNA following the first and last fraction of SBRT to quantify the magnitude of diversity of cfDNA as a marker of response to SBRT. We hypothesis that those patients with the highest fold change in ctDNA from peak level to nadir at first follow-up will have prolonged benefit from SBRT. We will monitor ctDNA levels during follow-up and at subsequent progression. We hypothesize that ctDNA will be useful to detect early relapse in the setting of SBRT.

20.1.3 Identification of circulating immune biomarkers of response to SBRT.

Abscopal responses, regression of lesions distant from the irradiated site, have been documented in patients treated with external beam radiotherapy. Immune responses as a result of antigen release or immunogenic cell death in the context of ionising radiation are thought to be responsible for this. We hypothesize that clinically translatable biomarkers of the immune response, detectable in the peripheral blood, will predict patient likely to have durable clinical benefit (disease control > 6 months) following SBRT.

The above translation studies will be supported by the analysis of paired pre and post treatment tissue biopsies (where available).

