	tumour-specific oncological intervention (e.g. change in					
	systemic therapy or localised non-SBRT radiotherapy) as					
	determined by the treating physician					
PRIMARY ENDPOINT	New or existing intra-cranial lesions not amenable to radical					
	surgery or SRS					
	• Development of new extra-cranial lesions or progression of					
	existing extra-cranial lesions not meeting the criteria for					
	SBRT treatment (e.g. size > 7cm)					
	 Development of >5 new or progressing extra-cranial lesions 					
	at any one point in time (i.e. widespread progression)					
	• Time to change in systemic therapy or clinical decision that					
	patient not suitable for further systemic therapy					
	Overall survival					
	 Patterns of disease progression 					
SECONDARY ENDPOINTS	 Radiotherapy toxicities (acute and late) using CTCAE 					
	Quality of Life					
	 Time to failure of next line of systemic therapy 					
	Measurement of resistant sub-clones in ctDNA					
	Deep sequencing analysis will be used to model tumour					
EXPLORATORY ENDPOINTS	evolution, neo-antigen burden and genomic instability in					
	paired tumour tissue at OPD baseline and at the time of					

	further progression (where available) in addition to ctDNA
	samples.
	 Where PET imaging has been undertaken (as per standard
	site practice), assessment of PET findings in relation to
	clinical outcome.
	All patients will be assessed 8 weeks post randomisation.
	Subsequent follow-up visits will be aligned with routine care and
FOLLOW UP	will occur at 3 monthly intervals from the end of treatment
	assessment visit.

HALT TRIAL SCHEMA

Follow-Up: All patients will be seen at 8 weeks post randomisation then every 3 months thereafter with tumour imaging and toxicity assessment occurring at each 3 monthly follow up visit until disease progression. QoL will be assessed at baseline, 8 weeks and at the first follow up visit. Patients will continue to be followed until death with information on current treatment and status being recorded at routine practice assessments.

Sample Collection: Blood samples will be collected from patients at baseline, after the first SBRT fraction (treatment group only), 8 weeks, 5 months and 8 months post-randomisation and upon progression. Archival tissue will be requested from all patients where available. Voluntary biopsies of progressive lesions will also be requested where possible.

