10.3 Post-treatment Follow-up

All patients will be assessed 8 weeks post randomisation and then subsequently at 3 monthly intervals (from 8 week assessment date) in line with routine care until disease progression is confirmed. The following assessments will be performed at each visit:

- Karnofsky Index and ECOG performance status
- Toxicity assessment including MRC dyspnoea score
- Post treatment QoL questionnaire (at 8 weeks post randomisation and first subsequent follow-up visit).
- Full blood count, urea, electrolytes and liver function tests (first 3 month visit only, not required thereafter)
- Tumour imaging assessment (imaging requirements at follow up visits will be determined by lesion location as identified at trial entry. The same imaging modality used at baseline should be used for subsequent follow-up assessments. Consideration should be given for repeat CT contrast/MRI brain as required)
- Current medication / treatment

Research blood samples will be taken at 8 weeks, 5 months and 8 months post-randomisation and upon progression (for patients randomised to receive SBRT an additional sample will be taken after delivery of the first fraction of SBRT).

Repeat SBRT – Only those patients allocated SBRT treatment at randomisation should be offered repeat SBRT treatment upon development of new OPD lesions or progression of existing extracranial lesions not progressing at trial entry, where the total number of progressing lesions at any one point remains ≤ 5 . Suitability of new OPD lesions for further SBRT will be based on the same criteria as at trial entry (visible, imaging defined targets suitable for SBRT, \leq 7cm). Where multiple lesions are treated over the course of the trial, composite dose volume data must be assessed and all normal tissue dose constraints need to be met by the composite plan. Particular caution is required where isodose lines overlap serial organs. Any previous radiotherapy before trial entry should also be taken into account. 50% isodose lines for plans to individual lesions should not overlap. A maximum of 5 thoracic lesions, 3 abdominal and 3 pelvic lesions can be considered for SBRT with composite planning confirming all normal tissue dose constraints are met.

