- Rectal Haemorrhage
- Haematuria
- Urinary frequency
- Urinary incontinence
- Urinary retention
- Urinary urgency

General

- Fever
- Fatigue
- Myelitis

Dermatology/Skin

- Dermatitis
- Hair loss (to treatment area)

Related to fiducial marker insertion

- Bleeding
- Sepsis (urinary and systemic)
- Pneumothorax

A7. Non-UK safety reporting requirements

The site Principal Investigator or designee is responsible for reporting SAEs to the ICR-CTSU as per the protocol.

[figure not shown]
The EORTC will report related unexpected SAEs as per national requirements to IECs and local investigators.

Further Sponsor safety reporting notification requirements will be agreed in the international site agreements.

HALT Protocol

ICR-CTSU

A8. Translational study collection (6 sampling points per patient)

GL DNA = Germ Line DNA (collected in EDTA tube)

cfDNA = circulating free tumour DNA (Streck tube)

RNA = RNA for analysis of T cell Repertoire from peripheral blood (1 x Tempus[™] blood RNA tube – 3ml blood draw)

FFPE Research Block: When available additional cores from biopsy of oligoprogressive lesions should be placed in a separate pot for fixation in FFPE at baseline and at the time of progression if biopsy was clinically indicated. Clinical diagnostic requirements take precedence.

HALT Protocol

ICR-CTSU

A9. GLOSSARY

AE	Adverse Event
ALT	Alanine Aminotransferase
ANC	Absolute Neutrophil Count
AST	Aspartate Aminotransferase
AUC	Area Under Curve
CI	Chief Investigator
CIS	Carcinoma In Situ
CRF	Case Report Form
DCF	Data Capture Form
DFS	Disease Free Survival
eCRF	Electronic Case Report Form
ECOG	Eastern Cooperative Oncology Group
EORTC	European Organisation for Research and Treatment of Cancer
FBC	Full Blood Count
G-CSF	Growth Colony-Stimulating Factors
GFR	Glomerular Filtration Rate
HR	Hazard Ratio
IB	Investigator's Brochure
ICR	The Institute Of Cancer Research
IDMC	Independent Data Monitoring Committee
LFT	Liver Function Test
MDT	Multi-disciplinary team
MRC	Medical Research Council
NCI CTCAE	National Cancer Institute Common Terminology Criteria for Adverse Events
OAR	Organs At Risk
PI	Principal Investigator
PIS	Patient Information Sheet
QoL	Quality of Life
R&D	Research and Development
RCT	Randomised controlled trial
RTTQA	NCRI Radiotherapy Trials Quality Assurance
SAE	Serious Adverse Event
SAR	Serious Adverse Reaction
SBRT	Stereotactic Body Radiotherapy
SMPC	Summary of Product Characteristics
SUSAR	Suspected Unexpected Serious Adverse Reaction

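### Section 20.1.2 plans a ctDNA measure after the last SBRT fraction and a peak-to-nadir fold change, but the six scheduled samples include no last-fraction draw and cannot identify a peak

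*Protocol*

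**What the plan says.** Section 20.1.2 of the protocol sets out the ctDNA kinetics work. It gives the biological premise, "The half life of ctDNA is 0.5-2 hours", then the measurement, "We intend to assess the release of ctDNA following the first and last fraction of SBRT", then the hypothesis that "those patients with the highest fold change in ctDNA from peak level to nadir at first follow-up will have prolonged benefit from SBRT".

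The operative sampling lists are elsewhere:

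- The trial schema: "Blood samples will be collected from patients at baseline, after the first SBRT fraction (treatment group only), 8 weeks, 5 months and 8 months" after randomisation, and again on progression.
- Section 10.3: "for patients randomised to receive SBRT an additional sample will be taken after delivery of the first fraction of SBRT". This is the only draw tied to an SBRT fraction.
- Section 10.7: the schedule has one column for the sample after fraction 1. Its footnote on research blood samples names the first fraction and no other.
- Appendix A8 is headed "Translational study collection (6 sampling points per patient").

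First follow-up is 8 weeks after randomisation, with a window of 5 days either side (section 10.7 footnotes). The readable text gives no clock window for the post-fraction-1 draw.

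**The concern.** Section 20.1.2 names two quantities that the sampling schedule has to supply: release after the last fraction, and a peak level. If a site can follow the schedule perfectly and still supply neither, the fault lies in the protocol, and no analysis plan can recover a sample that was never drawn.

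The stake is the test of the fold-change hypothesis. Someone would have to decide, once data exist, what stands in for the peak, and that leaves room for a choice guided by results. If post-fraction draws are taken at differing times, part of the spread between patients would also reflect draw time rather than release.

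**Working it through.** **Step 1: reproduce the stated number of samples.** The draws named in the schema, section 10.3 and section 10.7 are:

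1. baseline
2. after the first SBRT fraction (SBRT group only)
3. 8 weeks
4. 5 months
5. 8 months
6. progression

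The count is 6, which agrees with the A8 heading. Control patients have 6 − 1 = 5. A last-fraction draw would make 6 + 1 = 7 in the SBRT group and break the stated count. So no unallocated sample could serve as the last-fraction draw.

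**Step 2: can the samples give a peak?** The hypothesis needs "highest fold change in ctDNA from peak level to nadir at first follow-up". The follow-up end is covered by the 8-week sample. The peak end is a maximum over the hours after a fraction, and only one value is taken in that period. One value cannot show whether the level was still rising, at its highest or already falling. This holds whatever the half-life.

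**Step 3: how far does draw time matter?** Inputs:

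- Half-life h = 0.5 h and 2 h (section 20.1.2).
- Draw times of 15 minutes and 4 hours after the fraction: assumed for illustration.
- Background level B and released pulse P: not in the protocol, so a range is shown.
- Release is taken as instantaneous at the fraction, also an assumption. The protocol gives neither the time to peak nor the duration of release.

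The measured level at time t is M(t) = B + P × 2^(−t/h). The share of the pulse remaining is:

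| Time | h = 0.5 h | h = 2 h |
|---|---|---|
| 0.25 h | 2^(−0.5) = 0.707 | 2^(−0.125) = 0.917 |
| 4 h | 2^(−8) = 0.0039 | 2^(−2) = 0.25 |

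The ratio M(0.25)/M(4), for two patients with identical release, is:

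| Assumed pulse | h = 2 h | h = 0.5 h |
|---|---|---|
| P = B | (1 + 0.917)/(1 + 0.25) = 1.5 | (1 + 0.707)/(1 + 0.0039) = 1.7 |
| P = 10 × B | (1 + 9.17)/(1 + 2.5) = 2.9 | (1 + 7.07)/(1 + 0.039) = 7.8 |
| No background (B = 0) | 0.917/0.25 = 3.7 | 0.707/0.0039 = 181 |

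The last row is a limiting case. Patients enter with progressing disease, and section 1.8 takes detectable resistance mutations in ctDNA at that time as its premise, so zero background is not what the protocol expects. If release is delayed or sustained, all of these ratios change.

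**The case against.** The strongest reply is that only the phrase about the last fraction is irreconcilable, and that the rest is detail which section 13.3 leaves to the statistical analysis plan. The peak could be defined there as the highest value observed before first follow-up. That is possible, and release after the first fraction is indeed sampled. It would not be wrong to say that something can be calculated. What stands is that a highest-observed-value rule is a substitute for a peak and the protocol does not state it, while the last-fraction measure cannot be restored by any definition. If a course were given as a single fraction, first and last would coincide. The protocol leaves fractionation to a guideline that is not shown, and section 11.1 speaks of first and last fractions separately.

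Three stronger readings are tempting and are not supported:

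- **That the draw is untimed.** Under the A8 heading only a legend survives in the text available for this review. The collection chart is missing and may carry a window, as may the supplementary manuals mentioned in section 17.2. The chart cannot hold a last-fraction point without exceeding its own six, and one timed draw would still not identify a peak.
- **That draw time would dominate the ranking of patients, by up to about 180-fold.** That figure needs instantaneous release and no background ctDNA. The protocol supports neither.
- **That the gap of up to 4 weeks between baseline blood and SBRT, or TKI interruption at some centres, spoils the parameter.** The stated hypothesis runs from peak to first follow-up and does not use the baseline value. The protocol also gives no ctDNA growth rate from which such a drift could be sized.

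**Conclusion.** The point holds as an internal contradiction with a small consequence. Section 20.1.2 calls for a last-fraction measure that the schema, section 10.3, section 10.7 and the A8 count all exclude, and for a peak that one post-fraction draw cannot identify. This part rests on counting and needs no assumption.

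That the measured value depends on draw time follows from the protocol's half-life for any released pulse that is decaying. Its size is not known. The illustrative range is 1.5- to 7.8-fold for 15 minutes against 4 hours, under instantaneous release and a pulse of one to ten times background. Whether a draw window already exists outside the readable text is open.

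The severity is minor. ctDNA kinetics is an exploratory objective (section 2.3). The PFS and overall survival analyses do not use it. The comparison of ctDNA clearance in section 13.3 is a binary outcome that does not need a last-fraction sample or a peak.

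**What to change.** - In section 20.1.2, delete the reference to the last fraction and replace the peak level with the post-fraction-1 level. The parameter then becomes the fold change from the post-fraction-1 sample to the 8-week sample, which keeps the direction of the sponsor's hypothesis and uses draws that exist.
- Unless the A8 chart or a sample manual already does so, give the existing post-fraction-1 draw one fixed clock window in section 10.3, the section 10.7 footnote and A8, chosen with the stated half-life in mind. Record the end-of-fraction time and the draw time.
- If the sponsor does want release after the last fraction, the alternative is to schedule that draw and change the count of six in every place that lists it.

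The first two changes need no extra sample. They cost protocol wording and two time fields on the sample form. The downside is a tighter draw window for sites and a narrower exploratory hypothesis. Samples already taken without recorded times would not benefit from the window.

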20.2 Quality of Life study

Quality of Life (QoL) will be a secondary endpoint in the main trial and will be analysed as described in detail in the statistical analysis plan.

20.2.1 Quality of life measures

Patient reported outcomes will be measured using the EORTC QLQ C30 and the EQ-5D-5L. Patients will complete the EORTC QLQ C30 general cancer questionnaire and the EQ-5D-5L questionnaire, which is a brief standardised instrument that provides a simple descriptive profile of their health status.

20.2.2 Study design

Patients are eligible for the QoL/PRO study if they fulfil the HALT eligibility criteria. Participants will be asked in the patient information sheet to consent to regular completion of QoL/PRO questionnaires. Patients who decline to take part in the HALT QoL study will remain eligible for the main trial. QoL/PRO is a secondary endpoint in the main trial and the primary time point of interest is 8 weeks after randomisation for both groups of patients.

20.2.3 Timing of data collection

Participants will be asked to complete the questionnaires after informed consent is obtained during their clinic visit at the following time points; 1) before treatment allocation is known to the patient (treatment vs control group)), 2) 8 weeks post randomisation and 3) during the first 3 monthly follow-up visit.

20.2.4 Compliance

Missing data may hamper interpretation of PRO. Missing data may arise because participants do not complete the questionnaires at the appropriate time (unit non-response), or because patients may miss questions within the questionnaires (item non-response). During the study, compliance with PRO questionnaire completion will be monitored by the trial oversight committees.

20.2.5 Statistical considerations

Patient reported outcome analyses will be used to supplement results of clinician assessed treatment toxicity; therefore a formal sample size calculation has not been performed. An analysis plan will be developed in consultation with the TMG with key endpoints identified from each questionnaire. Standard algorithms will be used to derive scores and handle missing data in quality of life questionnaires. Quality of life data will be presented at individual time-points and analyses to account for the longitudinal nature of the data may be used.

